13.2 Sample Size/Accrual Rate

The data from the literature about survival of patients with advanced chondrosarcomas are almost non-existent. However, some studies confirm that the prognosis of patients with metastatic chondrosarcomas is poor and similar to that observed in metastatic soft-tissue tumors with median survival ranging from 7 to 17 months ([Dickey et al., 2004](#); [Ries et al., 2007](#); [Giuffrida et al., 2009](#)). Therefore, we believe that a 6 months clinical benefit rate of 40% is a reasonable objective in this setting. This objective was also chosen by American investigators (SARC) in a phase 2 trial of perifosine in patients with chemo-insensitive sarcomas (including chondrosarcomas).

We rely on an optimal two-stage Simon's design (Simon, 1989). Based on the following hypotheses under GDC-0449 treatment:

- 20% non-progression rate (null hypothesis),
- 40% acceptable non-progression rate (alternative hypothesis),
- 10% type I error rate,
- 90% power,

a total of 37 assessable subjects will be necessary, with 17 assessable subjects recruited to the first stage.

Stage 1: Following the inclusion of the first 17 assessable patients, if 3 or less patients are progression-free (complete response, partial response or stable disease), the study would be terminated early. Otherwise, the second group of 20 subjects will be recruited.

Stage 2: If at the end of recruitment, 11 patients or more are progression-free (out of the 37 evaluable patients), GDC-0449 would be considered worthy of further testing in this disease.

To be evaluable, a subject must meet the eligibility criteria AND have received at least one complete or two incomplete cycles of GDC-0449 AND at least one disease measurement recorded not less than eight weeks after treatment onset.

Given the disease is rare and the absence of standard treatment in this indication, inclusion will not be suspended after the recruitment of the first 17 patients. Inclusion will be pursued, while data on the first 17 patients will be analyzed.

In order to account for not evaluable patients (+/- 20%), **45 patients will be recruited.**

The anticipated accrual rate is 2-3 patients/months.

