11.1.8 Response Review

Review process

Independent response review involves:

1. Reviewing the disease status at 6 months (tumor evaluation at 6-months or earlier in case of disease progression) in comparison with baseline (primary objective).
2. Reviewing all responses (complete and partial) observed during the study period.

Independent response review will proceed as follows:

- The review process will be centralized at Institut Bergonié and will be performed by one independent radiologist expert in bone sarcomas.
- When reviewing the 6-month disease status, the reviewer will only be provided with the first 6-month patient information.
- Patient' files will be anonymous.

In case of discordance between the local radiologist and the reviewer, the judgment provided by the expert reviewer will be retained and used for response evaluation in statistical analyses.

Review process schedule

The Simon's two-stage ([section 13](#)) implies evaluating treatment efficacy after 17 patients at the first stage, and then once all 51 patients have been included.

Review will thus be implemented in two steps:

- Once 6-month information is available for the first 17 patients;
- At the end of the study.

Practical implementation

- Each site must send the completed “Baseline Clinical Subject Profile” ([Appendix JA](#)) with the first shipment.
- For each shipment, media should be accompanied by the completed “Radiology Referral Form” ([Appendix JB](#)).
- The reviewer will assess the response to therapy, document the results on the “Response Review Form” ([Appendix JC](#)) and sign this form.
- Patient’s information must be recorded on an imaging CD.
- Once 6-month response is available, each site must send the imaging CD to Institut Bergonié as soon as possible.
- Once complete patient’s follow-up has ended, an updated imaging CD must also be sent to Institut Bergonié
- All CDs must be sent to :

| |
|--|
| 
[name], Responsible Clinical research Assistant Institut Bergonié, [name], [name], France Phone: [name] – mail : [contact]
 |
|--|

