13. STATISTICAL CONSIDERATIONS

13.1 Study Design/Endpoint

We will rely on a two-stage Simon's design with the 6-month clinical benefit (CR + PR + SD) rate as the primary endpoint. At six months, patients will be classified as success (Alive at 6 months AND CR/PR/ SD) or failure (dead OR alive with progression).

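### The data cut for the final go/no-go count is stated inconsistently: section 13.2 ties it to the end of recruitment, while the endpoint is status at six months

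*Combined protocol and SAP*

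**What the plan says.** Section 13.1 fixes the endpoint in time: "At six months, patients will be classified as success (Alive at 6 months AND CR/PR/ SD) or failure", failure being death or progression.

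Section 13.2 states the design ("We rely on an optimal two-stage Simon's design", 17 + 20 = 37 evaluable patients) and the final rule: "If at the end of recruitment, 11 patients or more are progression-free (out of the 37 evaluable patients"), in which case the drug is worth further testing. The rule names a calendar event and a status, without a 6-month qualifier. The same section makes a patient evaluable only if a disease measurement exists at least eight weeks after treatment onset. Its stage-1 look is also worded by inclusion of 17 assessable patients.

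Section 11.1.8 says that the two-stage design implies evaluating efficacy after 17 patients and again when all patients, given there as 51, have been included. It then schedules the central review in two steps: "Once 6-month information is available for the first 17 patients", and "At the end of the study". Where local and central readings differ, the central one is used in the analyses.

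**The concern.** This is a single-arm trial whose one formal decision is a count of successes against a cut-off of 11 in 37. The binomial error rates hold only if each of the 37 contributes a 6-month outcome. On the day the last patient enters, the most recent entrants have been followed for days to months. An analyst who ran the count then would have to decide how to treat them, and the plan gives no rule. Some ways of counting make a false go much more likely; others make a true benefit easy to miss. The documents give at least two times for the final evaluation, end of inclusion and end of study, and neither is expressed in terms of the endpoint.

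**Working it through.** **1. Reproduce the design.** Inputs from 13.2: 20% against 40%, "10% type I error rate", 90% power, stop if 3 or fewer of 17, go if 11 or more of 37.

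P(go | p) = Σ over x = 4 to 17 of P[Bin(17, p) = x] × P[Bin(20, p) ≥ 11 − x]

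- p = 0.20: 0.0948 (probability of early stopping 0.549)
- p = 0.40: 0.9033 (probability of early stopping 0.046)

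A search over designs confirms 3/17, 10/37 as the optimal one. The stated figures are right when all 37 have a 6-month status.

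**2. Follow-up at last entry.** Accrual is 2-3 per month (13.2), and 37 of 45 recruited patients are expected to be evaluable (37/45 = 0.822).

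- Enrolled in the last six months: 6 × 2 = 12 to 6 × 3 = 18.
- Evaluable among them: 12 × 0.822 = 9.9 to 18 × 0.822 = 14.8, so about 10-15.
- At the pace implied by the 2-year inclusion period in section 1.3: 45/24 = 1.875 per month, giving 11.25 × 0.822 = 9.2.

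**3. Can 37 evaluable patients exist on that day?** Eight weeks is 56/30.44 = 1.84 months, in which 3.7 (at 2 per month) to 5.5 (at 3 per month) patients enter. That leaves 41.3 to 39.5 of 45 with eight weeks of follow-up; times 0.822, 34.0 to 32.5 are expected to be evaluable. On the plan's own numbers, 37 is not yet reached.

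**4. How many are truly undetermined?** A patient who has already progressed or died is a failure whatever the follow-up. The documents give no progression curve, so I assume an exponential one with the stated 6-month rate.

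- At 20%: hazard −ln(0.2)/6 = 0.268 per month; mean progression-free probability over 0-6 months is 0.8/1.609 = 0.497; times 9.9 to 14.8 gives 4.9 to 7.4. Counting evenly spaced entries one by one gives 5.3 to 7.8. About 5-8.
- At 40%: hazard 0.153; mean 0.6/0.916 = 0.655; 6.5 to 9.7. About 7-10.

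**5. Error rates if the count were made at last entry.** Further assumptions: 37 evaluable patients entering at even intervals, and stage 1 judged on full 6-month data.

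| How patients under 6 months are counted | Type I error at 2 / 2.5 / 3 per month | Power at 2 / 2.5 / 3 per month |
|---|---|---|
| Decision delayed until all have 6-month status | 9.5% / 9.5% / 9.5% | 90% / 90% / 90% |
| Everyone progression-free that day is a success | 36% / 40% / 42% | 95% / 95% / 95% |
| As above, but under 8 weeks is not a success | 10% / 14% / 14% | 88% / 91% / 90% |
| Anyone without 6 months is a failure | 1.1% / 0.4% / 0.2% | 54% / 35% / 23% |

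The second row counts patients whom 13.2 does not yet regard as evaluable, so it marks an upper limit and not an expected result.

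**The case against.** The best defence is that the phrase should be read within its section. Section 13.1 sets the classification at six months, 13.2 argues for a 6-month clinical benefit rate, and the eight-week condition means that the rule could not be run on the last day of recruitment. Stage 1 is also worded by inclusion in 13.2, yet 11.1.8 shows that it waits for 6-month information. With two years of inclusion in a four-year study (section 1.3), a review at study end falls about 24 months after the last planned entry, when every patient's 6-month status is long settled. This defence largely stands as to intent. It does not settle the text: 11.1.8 repeats the inclusion trigger, and no sentence states when the final count is made.

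Three stronger readings are tempting, and the documents do not support them.

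- A reader might infer that the decision will be made on incomplete data. That takes one phrase alone against 13.1 and the end-of-study review.
- A reader might infer that the late central review itself causes incomplete data. It does the opposite. It conflicts with the 13.2 timing, but one final central review is a legitimate choice.
- A reader might infer that the stage-1 boundary will be applied to the first 17 enrolled. If these yielded about 14 assessable patients, stopping at a true 40% would rise from 4.6% to 12.4% and power would fall to about 84%. But 13.2 defines stage 1 by 17 assessable patients and uses the shorter wording as shorthand, so this is hypothetical.

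**Conclusion.** The inconsistency is real: sections 13.1, 13.2 and 11.1.8 do not give one data cut for the final decision, and the rule in 13.2 cannot be carried out literally with the stated error rates. About 10-15 evaluable patients would be short of six months at last entry, with about 5-8 undetermined at a 20% rate and 7-10 at 40%.

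A reader might infer that the error always runs towards a false go. It does not. Type I error could be as high as about 36-42%, stay near 10-15%, or fall to about 1% or less with power of 54% down to 23%, depending on a counting convention that the plan does not state. The patient counts in steps 2 and 3 rest on the protocol's accrual and evaluability figures. The undetermined counts and the error rates also rest on the assumed exponential curve and even entry; they illustrate literal execution and do not predict what the sponsor will do. The sample size and both boundaries are sound.

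**What to change.** In section 13.2, reword the stage-2 rule along these lines: *when all 37 evaluable patients have a centrally read 6-month status or earlier failure, the drug is considered worth further testing if 11 or more are 6-month successes as defined in 13.1.* Word stage 1 the same way for the first 17 evaluable patients.

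In section 11.1.8, refer to the first 17 evaluable patients, use the same final trigger for the central reading of 6-month status, and reconcile the figure of 51 with the 45 recruited and 37 evaluable in 13.2. The review of best response can stay at the end of the study.

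The cost is a few sentences. The decision comes about six months after the last needed inclusion: later than the end of recruitment, but well before the end of a four-year study.

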| STUDY POPULATION Translational research study | All patients included in the trial are eligible for the translational research study. |
| NUMBER OF PATIENTS | Based on the following hypotheses under GDC-0449 treatment: 20% clinical benefit (null hypothesis), 40% acceptable clinical benefit (alternative hypothesis), 10% type I error rate, 90% power, a total of 37 assessable patients will be necessary (17 for the first stage + 20 for the second stage). In order to account for not assessable patients (+/- 20%), 45 patients will be recruited. |
| NUMBER OF SITES | This is a multicenter study. A complete list of investigators will be provided as a separate document. |
| STUDY DRUG FORMULATION | GDC-0449 – Capsules packaged in 75 mL bottles. Each bottle contains 32 capsules. |
| ROUTE OF ADMINISTRATION | GDC-0449: Oral |
| ADMINISTERED DOSE | GDC-0449: 150 mg, take with or without food at the same time every day |
| TREATMENT SCHEDULE | GDC-0449: Days 1-28 |

| | |
|---------------------------------------|--|
| EFFICACY EVALUATIONS | 
Patients will be evaluated for efficacy if they receive at least one complete or two incomplete cycles of GDC-0449, and if they have at least one disease measurement recorded not less than eight weeks after treatment onset (except for in case of early disease progression).
 
Antitumor activity will be assessed using RECIST on a set of measurable lesions identified at baseline as target lesions and followed until disease progression by the appropriate method (computed tomography [CT] scan or magnetic resonance imaging [MRI]).
 
Radiological and clinical (whenever appropriate) tumor assessment will be performed at baseline and every eight weeks until evidence of disease progression (PD). Whenever the criteria of response are met, the appropriate imaging tests will be repeated at least four weeks later in order to confirm the response. Beyond 48 months of treatment without evidence of progressive disease, radiological tumor assessment will be performed every 3 months.
 
Efficacy will be evaluated based on 6-month clinical benefit rate (primary objective), best overall response, 1- and 2-year PFS, and 1- and 2-year OS.
 |

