| CR | SD | SD provided minimum criteria for SD duration met, otherwise, PD |
| CR | PD | SD provided minimum criteria for SD duration met, otherwise, PD |
| CR | NE | SD provided minimum criteria for SD duration met, otherwise NE |
| PR | CR | PR |
| PR | PR | PR |
| PR | SD | SD |
| PR | PD | SD provided minimum criteria for SD duration met, otherwise, PD |
| PR | NE | SD provided minimum criteria for SD duration met, otherwise NE |
| NE | NE | NE |

CR = complete response, PR = partial response, SD = stable disease, PD = progressive disease, and NE = inevaluable.
^a If a CR is truly met at first time point, then any disease seen at a subsequent time point, even disease meeting PR criteria relative to baseline, makes the disease PD at that point (since disease must have reappeared after CR). Best response would depend on whether minimum duration for SD was met. However, sometimes 'CR' may be claimed when subsequent scans suggest small lesions were likely still present and in fact the patient had PR, not CR at the first time point. Under these circumstances, the original CR should be changed to PR and the best response is PR.

Special notes on response assessment

When nodal disease is included in the sum of target lesions and the nodes decrease to ‘normal’ size (<10 mm), they may still have a measurement reported on scans. This measurement should be recorded even though the nodes are normal in order not to overstate progression should it be based on increase in size of the nodes. As noted earlier, this means that patients with CR (complete response) may not have a total sum of ‘zero’ on the case report form (CRF).

In trials where confirmation of response is required, repeated ‘NE’ time point assessments may complicate best response determination. The analysis plan for the trial must address how missing data/assessments will be addressed in determination of response and progression. For example, in most trials it is reasonable to consider a patient with time point responses of PR-NE-PR as a confirmed response.

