Patients with a global deterioration of health status requiring discontinuation of treatment without objective evidence of disease progression at that time should be reported as ‘symptomatic deterioration’. Every effort should be made to document objective progression even after discontinuation of treatment. Symptomatic deterioration is *not* a descriptor of an objective response: it is a reason for stopping study therapy. The objective response status of such patients is to be determined by evaluation of target and non-target disease as shown in Tables belows.

Table 1 – Time point response: patients with target (+/- non-target) disease.

| Target lesions | Non-target lesions | New lesions | Overall response |
|-------------------|-----------------------------|-------------|------------------|
| CR | CR | No | CR |
| CR | Non-CR/non-PD | No | PR |
| CR | Not evaluated | No | PR |
| PR | Non-PD or not all evaluated | No | PR |
| SD | Non-PD or not all evaluated | No | SD |
| Not all evaluated | Non-PD | No | NE |
| PD | Any | Yes or No | PD |
| Any | PD | Yes or No | PD |
| Any | Any | Yes | PD |

CR = complete response, PR = partial response, SD = stable disease, PD = progressive disease, and NE = inevaluable.

Table 2 – Time point response: patients with non-target disease only.

| Non-target lesions | New lesions | Overall response |
|--------------------|-------------|----------------------------|
| CR | No | CR |
| Non-CR/non-PD | No | Non-CR/non-PD ^a |
| Not all evaluated | No | NE |
| Unequivocal PD | Yes or No | PD |
| Any | Yes | PD |

CR = complete response, PD = progressive disease, and NE = inevaluable.
^a a ‘Non-CR/non-PD’ is preferred over ‘stable disease’ for non-target disease since SD is increasingly used as endpoint for assessment of efficacy in some trials so to assign this category when no lesions can be measured is not advised.

Conditions that define ‘early progression, early death and inevaluability’ are study specific and should be clearly described in each protocol (depending on treatment duration, treatment periodicity).

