14.2.3. Handling of missing data

The monitoring of data for adverse events will be carried out regularly in order to effectively limit the amount of missing data likely to prevent or hamper trial implementation and analysis.

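### Section 13.2 requires a week-8 measurement before a patient enters the Simon counts, so it can drop early failures that Section 13.1 counts, but never a 6-month success

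*Combined protocol and SAP*

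**What the plan says.** Section 13.2 sets a 20% null and a 40% alternative, 10% type I error and 90% power, and asks for 37 assessable patients, 17 of them in stage 1. The trial stops if 3 or fewer of 17 are progression-free and is positive if at least 11 of 37 are. To be evaluable, a patient must be eligible, must have received one complete or two incomplete cycles, "AND at least one disease measurement recorded not less than eight weeks after treatment onset". No exception is stated. Forty-five patients are recruited to allow for those who are not evaluable.

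Five other places bear on the same count:

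- **Section 13.1** classifies each patient at six months as a success (alive with CR, PR or SD) "or failure (dead OR alive with progression").
- **The synopsis** (efficacy evaluations) repeats the cycle and week-8 conditions but adds "except for in case of early disease progression". It does not mention early death.
- **Section 11.1.8** bases the review for the primary objective on "tumor evaluation at 6-months or earlier in case of disease progression". It also places the final evaluation "once all 51 patients have been included", against 45 in 13.2.
- **Sections 11.1.1 and 13.5.2** keep the cycle minimum but have no week-8 condition. They govern the main analysis of the response rate, and the documents do not say whether that is the primary endpoint. Section 13.5.2 lists three early-death categories without saying how they enter the Simon counts.
- **Section 11.1.4** says that the conditions defining early progression, early death and inevaluability "are study specific and should be clearly described in each protocol". Section 14.2.3, on missing data, describes only data monitoring "in order to effectively limit the amount of missing data".

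**The concern.** A patient who completes cycle 1 and dies at week 6 is a failure under 13.1 but lies outside the 17 and the 37 under 13.2. A patient whose progression is documented before week 8, with no later scan, is also outside under 13.2, but inside under the synopsis and 11.1.8. Because 45 are recruited for 37, such a patient's place can be filled by someone else.

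The error runs one way. A 6-month CR, PR or SD needs a tumor evaluation at about six months, so every success already meets the week-8 condition. The condition can exclude only failures and patients who were never assessed. Both the stage-1 stop and the final decision then rest on a denominator from which some early failures have been taken out, and two analysts following different sections could reach opposite conclusions from the same data.

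**Working it through.** **1. The plan's own design.** Inputs from 13.2: p0 = 0.20, p1 = 0.40, stop if X1 ≤ 3 of 17, positive if the total is ≥ 11 of 37.

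P(positive | p) = Σ over x = 4 to 17 of P(X1 = x) × P(X2 ≥ 11 − x), with X1 ~ Bin(17, p) and X2 ~ Bin(20, p).

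- p = 0.20: type I error 0.0948; probability of stopping at stage 1, 0.549.
- p = 0.40: power 0.903.

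The stated design is reproduced. A search over all two-stage designs also returns 3/17 and 10/37 as the optimal one. The margin below the 10% limit is 0.0052.

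**2. Removing early failures, if the 20% null describes all eligible treated patients.** Suppose k of 45 are early failures that are removed and replaced. All are failures, so the success rate among those kept is 0.20 / (1 − k/45). The documents do not give k; these values are assumptions.

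| k of 45 | Null rate among those kept | Type I error | Stage-1 stop under the null |
|---|---|---|---|
| 0 | 0.2000 | 0.0948 | 0.549 |
| 1 | 0.2045 | 0.107 | 0.530 |
| 2 | 0.2093 | 0.122 | 0.510 |
| 4 | 0.2195 | 0.156 | 0.469 |

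**3. If the 20% null describes assessable patients only.** The rate among those kept is 0.20 by definition, so type I error stays at 0.0948. What remains is that the reported rate overstates the rate in treated patients, by the factor 1 / (1 − k/45): 1.047 at k = 2 and 1.098 at k = 4.

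**4. How a decision can change.** Take 37 eligible patients who all meet the cycle minimum, with 10 successes and 2 deaths before week 8 without documented progression. Under 13.1 the result is 10/37, negative. Under 13.2, and under the synopsis, the two deaths are replaced. The chance of at least one success among two replacements at a 20% rate is 1 − 0.8² = 0.36, and one success gives 11/37, positive. The case is borderline by construction; it shows that a change is possible, not how often it happens.

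**5. Who is affected under each wording.**

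| Patient who meets the cycle minimum | 13.1 | 13.2 as written | Synopsis |
|---|---|---|---|
| Dies before week 8, no documented progression | Failure | Not evaluable | Not evaluable |
| Progression before week 8, no later measurement | Failure | Not evaluable | Evaluable |
| Progression seen at a scan at week 8 or later | Failure | Evaluable | Evaluable |
| Alive, no 6-month assessment | Not classified | Depends on week-8 scan | Depends on week-8 scan |

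**The case against.** The strongest reply is that 13.2 moves from its hypotheses directly to a number of assessable subjects, and the synopsis does the same. The natural reading is then that 20% and 40% describe assessable patients. This stands. A reader might infer that the trial's type I error is 0.107 to 0.156, but the documents do not support that as an unconditional statement.

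A second reply is that much is handled elsewhere. The synopsis and 11.1.8 keep early progressors, 13.5.2 assesses all included patients, and the life-expectancy criterion (more than 3 months) makes early deaths fewer. This narrows the group but does not close the gap. If the synopsis governs, mainly deaths before week 8 without documented progression remain, and no section places those in the Simon denominator.

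Two further inferences are tempting and should not be drawn:

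- **Sizing k from the survival medians in 13.2.** With exponential survival and medians of 7 to 17 months, 1 − 0.5^(0.92/7) = 8.7% to 1 − 0.5^(0.92/17) = 3.7% of patients alive at week 4 would die in the next four weeks (0.92 months), or 3.9 to 1.7 of 45. This is not an upper limit for 13.2 as written, which also removes early progressors with no later scan. Nor is it a forecast, given the life-expectancy criterion.
- **Reading 11.1.4 as an unmet duty for the primary endpoint.** The sentence "The analysis plan for the trial must address how missing data/assessments will be addressed in determination of response and progression" stands in a note on confirming best response, which is a secondary endpoint. The statement in the same section on early death and inevaluability is the relevant one.

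The cycle minimum is common to all four definitions and is not in conflict.

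**Conclusion.** The contradiction is in the text and concerns the denominator of the primary decision rule. Its direction is certain: the week-8 condition can raise the observed rate and weaken both Simon rules, never the reverse. Its size is not known. Type I error of 0.107, 0.122 or 0.156 rests on two assumptions: that the 20% null applies to all eligible treated patients, and that 1, 2 or 4 of 45 are removed. On the assessable-only reading the error rate is as designed and the consequence is an overestimate for treated patients. Either way the primary denominator is left open. This should be fixed. Confidence is high for the inconsistency and its direction, and conditional for the error inflation.

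**What to change.** Use one evaluability definition in the synopsis, 11.1.1, 13.2 and 13.5.2:

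- Any eligible patient in the primary analysis set who dies or progresses before 6 months is evaluable and counts as a failure in both the 17 and the 37, whether or not a week-8 measurement exists.
- Treat the cycle minimum the same way for successes and failures. Either keep it for all, or drop it for all and take every eligible patient with at least one dose. Waiving it only for failures would create the opposite bias.
- Count patients alive without a 6-month assessment as failures in the primary analysis.
- Apply 3/17 and 11/37 to the first 17 and first 37 evaluable patients in order of inclusion. Do not apply a cutoff of 11 to all 45: after the same stage 1, that gives type I error 0.215.
- Report the rate under the current 13.2 definition as a sensitivity analysis.
- Reconcile the 51 patients in 11.1.8 with the 45 in 13.2.

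**Cost.** No new data are needed, but 15.1 requires an amendment approved by the ethics committee and ANSM. If it is made after data are known, the revised analysis should be labelled as such. The reported rate will be somewhat lower. If the 20% and 40% were meant for assessable patients only, counting early failures multiplies both by 1 − k/45. Power with 11/37 then falls from 0.903 to 0.864 at k = 2 (rate 0.382) or 0.814 at k = 4 (rate 0.364), with type I error 0.073 or 0.055. This loss below the stated 90% should appear beside the change. Counting unassessed patients as failures also costs power: 0.858 if 5% of true successes lack a 6-month assessment, 0.799 if 10% do.

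### The stage-1 futility result is certain at the 14th failure among the first 17 assessable patients, but the plan waits for 6-month data on all 17 while accrual runs on

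*Combined protocol and SAP*

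**What the plan says.** Section 13.2 of the combined protocol and SAP sets an optimal Simon design: "a total of 37 assessable subjects will be necessary, with 17 assessable subjects recruited to the first stage". At stage 1, "if 3 or less patients are progression-free (complete response, partial response or stable disease), the study would be terminated early". The same section gives rarity and the lack of a standard treatment as the reason why "inclusion will not be suspended after the recruitment of the first 17 patients"; recruitment goes on while the first 17 are analysed, towards a total of 45.

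Section 11.1.8 schedules the central review in two steps. The first is "Once 6-month information is available for the first 17 patients" and the second is at the end of the study. Where the central and local readings differ, the central one is used in the analysis. The same section defines the status under review as the 6-month evaluation, or a sooner one if the patient has progressed.

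Section 13.1 counts death or progression by 6 months as failure. Section 11.1 sets scans every 8 weeks. Nothing provides for a decision before the stage-1 batch review, or for a limit on enrolment during the wait other than the total of 45.

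**The concern.** An optimal two-stage design is chosen to keep the expected number of patients low when the drug is inactive. That benefit depends on how many patients have entered by the time the futility decision is made. With accrual open, six months at 2-3 per month adds 12-18 patients beyond stage 1.

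The stated reason supports not pausing accrual. It does not support waiting for a result that is already fixed. Success is known only at 6 months, but failure is known when it happens, and futility at stage 1 is determined by failures alone. What is at stake is the number of patients who start a drug after the trial's own rule can no longer be passed.

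**Working it through.** **1. The plan's design.** Inputs from 13.2: null rate 0.20, alternative 0.40, type I error 0.10, power 0.90, stop at 3/17 or fewer, positive at 11/37 or more. With X1 ~ Bin(17, p) and X2 ~ Bin(20, p):

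- P(positive) = sum over x = 4 to 17 of P(X1 = x) × P(X2 ≥ 11 − x). This gives 0.0948 at p = 0.20 and 0.9033 at p = 0.40.
- P(stop at stage 1 | 0.20) = P(X1 ≤ 3) = 0.549.
- E[N | 0.20] = 17 + 20 × (1 − 0.549) = 26.0.

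Exact enumeration confirms 3/17, 10/37 as the optimal design, so the plan's figures are reproduced.

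**2. Why the decision is the same.** Three or fewer successes among 17 is the same event as 17 − 3 = 14 or more failures among those 17. A failure under 13.1 cannot be reversed. The 14th failure therefore occurs if and only if the full look would stop the trial. Simulation found no mismatch in any setting, and the three probabilities above are unchanged.

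This holds only if failures are counted among the first 17 assessable patients in order of inclusion. Counting the first 14 failures by calendar date among all assessable patients changed the decision in 18-31% of trials at the null.

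**3. Patients enrolled at each look.** From the documents: 2-3 patients per month, cap of 45, 8-week scans, not-evaluable allowance of 0 or 8/45 = 17.8%. Assumed, because the documents give no figure: Poisson accrual, exponential failure times set to the 6-month rate, a true rate of 20% or 10%, and evaluability known at entry and unrelated to outcome. There were 15,000 simulated trials per setting. The table shows means in trials that stop.

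| True rate | Per month | Not evaluable | 17th + 6 months | All 17 classified | 14th failure | Saving vs 17th + 6 | Saving vs classified |
|---|---|---|---|---|---|---|---|
| 20% | 2 | 0 | 29.0 | 26.8 | 23.7 | 5.3 | 3.1 |
| 20% | 2 | 17.8% | 32.7 | 30.3 | 27.1 | 5.6 | 3.2 |
| 20% | 3 | 0 | 35.0 | 32.4 | 28.4 | 6.6 | 4.0 |
| 20% | 3 | 17.8% | 38.5 | 35.8 | 31.5 | 7.0 | 4.3 |
| 10% | 2 | 0 | 29.0 | 26.1 | 21.9 | 7.1 | 4.2 |
| 10% | 2 | 17.8% | 32.7 | 29.6 | 25.1 | 7.5 | 4.5 |
| 10% | 3 | 0 | 35.0 | 31.5 | 25.9 | 9.1 | 5.6 |
| 10% | 3 | 17.8% | 38.5 | 34.8 | 28.9 | 9.6 | 5.9 |

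Hand check of the first look: 17 + 6 × 2 = 29 and 17 + 6 × 3 = 35. With 17.8% not evaluable, 17/(37/45) = 20.7, and 20.7 + 12 = 32.7.

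**4. Averaged over all trials at the null.** About 55% stop, and the others save nothing: 0.55 × 5.3 = 2.9 and 0.55 × 7.0 = 3.8 patients, against the look at the 17th patient + 6 months.

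**5. Sensitivity at a true rate of 20%, same baseline.** Later-clustered failures (Weibull shape 1.5) give about 4-5. If failures became known only at 6 months, the saving would be about 1. Each month of confirmation delay that affects only the rolling reads removes about 2-3 patients from the saving, which is one month of accrual.

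**The case against.** The strongest objection concerns the baseline. Section 11.1.8 accepts an evaluation before 6 months when a patient has progressed, so the planned look can fall when all 17 are classified and need not wait for the 17th patient to reach 6 months. That reading is reasonable, and it lowers the saving to about 3-4 patients at the null. It stands, and both readings are reported here.

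The timing of failures is also assumed: section 13.2 itself says that survival data in this disease are almost absent. Section 11.1.4 lets equivocal progression wait for the next scheduled scan and leaves progression in non-target lesions alone to later confirmation. Both would delay the usable 14th failure.

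Rolling reads are not free either. Scans must be shipped and read as they arrive, and individual calls by a single central reader could close the trial. That reader's judgement already decides stage 1, but the effect of each call would be more immediate.

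Finally, it can be said that nothing here is an error: the design is correctly calculated, open accrual is disclosed with a reason, enrolment is capped at 45, and the Steering Committee assesses benefit and risk during the trial (14.1.1). That is true. None of it removes the gain, because no provision lets the decision be taken when it is already determined.

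**Conclusion.** The point holds as an inexpensive improvement to a correctly calculated design. Stopping at the 14th failure among the first 17 assessable patients gives the identical decision and leaves type I error, power and stopping probability unchanged. In trials that stop, it enrols about 5-7 fewer patients at a true rate of 20% and 7-10 fewer at 10% against a look at the 17th patient + 6 months. Against a look once all 17 are classified, the figures are about 3-4 and 4-6. Averaged over all trials at the null, the saving is about 3-4 on the first reading. The equivalence is exact. The sizes rest on the accrual, evaluability and failure-time assumptions above, and later-clustered failures or confirmation lag reduce them.

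Two stronger readings are tempting and should not be drawn. A reader might infer a flat saving of 6-10 patients. That range needs a trial that stops, the later of the two look dates and, at its upper end, a true rate well below the 20% null, which the documents do not posit. A reader might also infer that open accrual damages the error rates. It does not: the rule is applied to the same 17 patients whenever it is read.

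**What to change.** - **Section 13.2.** Add text such as: *Accrual continues during stage 1. The study stops for futility as soon as 14 of the first 17 evaluable patients, taken in order of inclusion and not in calendar order of failure, have centrally confirmed progression or have died within 6 months.*
- **Section 11.1.8.** Have the same reviewer read stage-1 progression scans as they arrive. The 6-month reads of the remaining stage-1 patients stay as planned if the boundary has not been reached.
- **Evaluability.** Reconcile the synopsis (Efficacy Evaluations), which exempts early progression from the requirement for a measurement at 8 weeks or later, with 13.2, which does not. Until this is settled the first 17 are not defined, either for the present look or for curtailment. A failure should count only once it is certain that the patient belongs to the first 17.

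The cost is protocol wording, rolling shipment and reading of scans in place of one batch, and slightly fewer patients for the secondary analyses when the trial stops. No extra patients are needed and accrual need not pause.
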